12.1.3.2. Statistical Methods

All implanted and randomized subjects will contribute to the analysis of Secondary Endpoint 2. Cox proportional hazards modeling will be performed, with time-to- death used as the outcome and programming scheme used as the covariate in the model. Traditional therapy will be considered the reference group in the analysis. Each subject's death will contribute to the analysis. Subjects that survived the follow-up duration will be censored at their date of withdrawal, study exit or on the date of the data snapshot, whichever occurs first. From the Cox model, the hazard ratio and corresponding confidence interval for programming scheme will be calculated. If the confidence interval for the hazard ratio is fully contained within the equivalence region – between 0.65 and 1.54 – equivalence of shocks only and standard programming will be concluded. In the event that equivalency cannot be established, superiority testing will be performed, employing similar methodology to that described for the Primary Endpoint.

12.1.4. Secondary Endpoint 3 – Time-to-First Appropriate Shock

The incidence of appropriate shocks in subjects programmed with shocks only will be compared with subjects programmed to standard therapy (ATP and shock) to assess equivalency.

12.1.4.1. Hypotheses

The hazard ratio of appropriate shocks will be used to evaluate the equivalence of shocks only programming and standard therapy. A relative equivalence margin of 35% in each direction will be employed. The following hypotheses will be used.

 H_0 : Hazard Ratio ≤ 0.65 or Hazard Ratio $\geq (1/0.65)$

 H_A : 0.65 < Hazard Ratio < (1/0.65)

12.1.4.2. Statistical Methods

All implanted and randomized subjects will contribute to the analysis of Secondary Endpoint 3. Cox proportional hazards modeling will be performed, with time-to-first appropriate shock therapy episode used as the outcome and programming scheme used as the covariate in the model. Traditional therapy will be considered the reference group in the analysis. Each subject's first appropriate shock therapy episode will contribute to the analysis. Subjects without an appropriate shock therapy episode will be censored at their date of death, withdrawal, study exit or on the date of the data snapshot, whichever occurs first. From the Cox model, the hazard ratio and corresponding confidence interval for programming scheme will be calculated. If the confidence interval for the hazard ratio is fully contained within the equivalence region – between 0.65 and 1.54 – equivalence of shocks only and standard programming will be concluded. In the event that equivalency cannot be established, superiority testing will be performed, employing similar methodology to that described for the Primary Endpoint.

12.1.5. Secondary Endpoint 4 – Time-to-First Inappropriate Shock

The incidence of inappropriate shocks in subjects programmed with shocks only will be compared with subjects programmed to standard therapy (ATP and shock) to assess equivalency.

12.1.5.1. Hypotheses

The hazard ratio of inappropriate shocks will be used to evaluate the equivalence of shocks only programming and standard therapy. A relative equivalence margin of 35% in each direction will be employed. The following hypotheses will be used.

H₀: Hazard Ratio ≤ 0.65 or Hazard Ratio $\geq (1/0.65)$

 H_A : 0.65 < Hazard Ratio < (1/0.65)

12.1.5.2. Statistical Methods

All implanted and randomized subjects will contribute to the analysis of Secondary Endpoint 4. Cox proportional hazards modeling will be performed, with time-to-first inappropriate shock therapy episode used as the outcome and programming scheme used as the covariate in the model. Traditional therapy will be considered the reference group in the analysis. Each subject's first inappropriate shock therapy episode will contribute to the analysis. Subjects without an inappropriate shock therapy episode will be censored at their date of death, withdrawal, study exit or on the date of the data snapshot, whichever occurs first. From the Cox model, the hazard ratio and corresponding confidence interval for programming scheme will be calculated. If the confidence interval for the hazard ratio is fully contained within the equivalence region – between 0.65 and 1.54 – equivalence of shocks only and standard programming will be concluded. In the event that equivalency cannot be established, superiority testing will be performed, employing similar methodology to that described for the Primary Endpoint.

12.1.6. Tertiary Objectives

12.1.6.1. Multivariate analyses

The purpose of this tertiary objective is to determine covariates associated with the use of ATP, bradycardia pacing, and the need for future CRT-D pacing therapy. The number of sustained VT episodes that occur in the monitor only zone and the percentage of patients that have these events will also be evaluated. Each outcome will be assessed separately, resulting in three separate multivariate Cox proportional hazards models. Covariates considered for inclusion in the final multivariate models include, but are not limited to, the characteristics listed in Section 12.3.2.

12.1.6.2. Latitude Alerts

The purpose of this tertiary objective is to (1) characterize the usage rates of HeartLogic among study patients, (2) characterize the alert rates among patients using HeartLogic, and (3) evaluate if usage and/or alerts are associated with changes in clinical therapy, the occurrence of adverse events, or other patient outcomes.

12.2. General Statistical Methods

12.2.1. Analysis Sets

All primary and secondary endpoint analyses will be performed following intention-to-treat (ITT) methodology, in which each subject is analyzed per their intended (i.e., randomized) treatment assignment. An as-treated analysis may be performed as well, in which subjects would be analyzed per the treatment received and may be time-varying to accommodate cross-overs. A per-protocol analysis may also be performed, limited to the subjects that adhered to important protocol criteria. This list of criteria will be defined prior to analysis, but not necessarily prior to the start of the study, to allow for knowledge gained throughout the study execution to be reflected in the analysis.

12.2.2. Control of Systematic Error/Bias

Overall Type I error for the Primary Endpoint will not exceed 5%. Type I error will be split and managed for the interim superiority analyses by employing an O'Brien-Fleming-type error spending function. Superiority testing for each group will be performed with an overall Type I error of 2.5%, resulting in a total of 5% across both groups. As described in Section 12.1.1.3, in the event that equivalency is not established, Type I error will be controlled for the additional superiority test per gating methodology and will not require further multiplicity adjustments

To reduce the possible introduction of selection bias, subjects will be randomized to their treatment assignment. To reduce the possible introduction of observer bias, an objective primary outcome of device-recorded all-cause shocks will be evaluated. To reduce the possible introduction of classification bias for the secondary endpoints of appropriate and inappropriate shocks, shocks will be adjudicated by an independent electrogram adjudication core lab.

12.2.3. Number of Subjects per Investigative Site

No single site is to enroll more than 10% (260 patients) without the prior written approval from the sponsor or sponsor's delegated representative.

12.3. Data Analyses

12.3.1. Interim Analyses

Interim analyses will be performed to assess the superiority of shocks only or standard programming. Four analyses (three interim analyses and one final) are planned. The Type I error/alpha spending will be managed using an O'Brien-Fleming-type error spending function. The following alpha will be allocated for each analysis.

Analysis Number	Information Proportion at Time of Analysis	Cumulative Type I Error (Alpha) Spending	Significance Level Used for Analysis*
1	0.25	0.00001	0.00000736681
2	0.50	0.00153	0.00152000000
3	0.75	0.00965	0.00916000000
4	1.00	0.02500	0.02200000000
*If D	valua is loss than specified sie	anificance level superiority	will be determined

^{*}If P-value is less than specified significance level, superiority will be determined.

12.3.2. Subgroup Analyses

Analyses will be performed to assess whether significant interactions exist between randomization group and various baseline characteristics. Analyses will evaluate, but are not limited to, the following baseline characteristics and their corresponding subgroups.

Characteristic	Subgroup 1	Subgroup 2
Age	≥ 65	< 65
Gender	Female	Male
History of Atrial Fibrillation	AF	No AF
Ischemic Status	Ischemic	Non-Ischemic
Diabetes	Diabetic	Non-diabetic

Regardless of the results of the interaction test for each characteristic, analyses of each subgroup will be performed. Analyses will be conducted for the Primary Endpoint and all Secondary Endpoints.

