8.2. Treatment Assignment

Any patient meeting all inclusion and no exclusion criteria is enrollment eligible for the APPRAISE ATP study. Patients are considered enrolled in the study once the informed consent form (ICF) has been executed.

Randomization schemes can be obtained by logging onto the electronic data capture system (EDC) and registering the patient. Randomization will be in a 1:1 ratio of either treatment arm and will be stratified by ischemic etiology, history of atrial fibrillation, and diabetes.

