9.2. Inclusion Criteria

Subjects who meet all of the following criteria (see Table 9.2-1) may be given consideration for inclusion in this clinical investigation, provided no exclusion criterion (see Section 9.3) is met.

Table 9.2-1: Inclusion Criteria

Clinical Inclusion Criteria	Subject with a Boston Scientific transvenous ICD (de novo implant or upgrade from pacemaker to ICD) implanted because of one of the following:
	 Prior MI and left ventricular ejection fraction (LVEF) less than or equal to (≤)30% OR Ischemic or non-ischemic cardiomyopathy, and LVEF ≤ 35%, and NYHA class II or III
	 Subject is age 21or above, or is considered of legal age per given geography Subject is willing and capable of providing informed consent Subject is willing and capable of complying with follow-up visits as defined by this protocol

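### The arm-by-age interaction is specified only with age split at 65; testing age as continuous would keep roughly 25–42% more of the information if the effect is about linear in age

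*Combined protocol and SAP*

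**What the plan says.** Section 12.3.2 (Subgroup Analyses) plans interaction tests: "Analyses will be performed to assess whether significant interactions exist between randomization group and various baseline characteristics". It continues: "Analyses will evaluate, but are not limited to, the following baseline characteristics and their corresponding subgroups". The table beneath lists five characteristics, each with two subgroups: age (65 and over, under 65), gender, history of atrial fibrillation, ischemic status and diabetes. Age is the only one of the five that is naturally continuous. The section adds that each subgroup will be analysed whatever the interaction test shows, and on scope it says: "Analyses will be conducted for the Primary Endpoint and all Secondary Endpoints". That covers the primary endpoint and four secondary endpoints.

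Nothing in the design requires the cut. Section 8.2 has randomization "stratified by ischemic etiology, history of atrial fibrillation, and diabetes", so age is not a stratum. Demographics are collected at enrollment (Tables 11.1-1 and 11.1-2), and the eligibility rule in Section 9.2 already needs the subject's age: "Subject is age 21or above, or is considered of legal age per given geography".

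**The concern.** Splitting age at 65 treats subjects aged 40 and 64 as alike and subjects aged 64 and 66 as different. If the effect of omitting ATP varies gradually with age, a test on two groups uses less of the available information than a test on age itself.

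The direction of the loss matters here because the trial hopes to conclude equivalence. A non-significant interaction is likely to be read as support for applying that conclusion at all ages. Avoidable loss of power makes such a result more likely even when the effect does vary with age. Appropriate and inappropriate shocks are components of all-cause shock, so neither can have more first events than the primary endpoint. Interaction tests on them start from less information still.

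**Working it through.** **Inputs from the documents.** Cut at 65 (Section 12.3.2); 1:1 randomization, not stratified by age (Section 8.2); 2600 subjects, margin 0.65 to 1/0.65, 90% power, 10% attrition at 18 months, 42-month enrollment (Section 12.1.1.2); final significance level 0.022 (Section 12.3.1).

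**Assumptions.** The documents give no age distribution, no shape for an age effect and no significance level for interaction tests. I assume an effect linear in age on the log hazard ratio and a two-sided 5% test, and vary the age distribution.

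**Step 1: the plan's own figure.** The plan states no information loss for the age split; its related figure is the sample size. Two one-sided tests at a true hazard ratio of 1 need 4 × (2.014 + 1.645)² / (ln 0.65)² = 288.6 events at 0.022 per side. Suppose the 6% and 7% shock rates are 18-month cumulative rates, with exponential shock and attrition times and uniform enrollment. Then 2600 subjects give 288.1 events in scenario 1 and 289.7 in scenario 2, which reproduces the sample size. The time unit of those rates is not stated; read as annual rates they give about 418 and 420 events. The percentages and powers in Steps 2 and 3 do not depend on the event count.

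**Step 2: information kept by the split.** Relative to a linear term, a two-group split keeps the squared correlation between age and the group indicator. Let p be the proportion under 65.

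- Normal age: φ(c)² / [p(1 − p)], with c = (65 − mean)/SD.
- Flat age: 3p(1 − p).

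| Assumed age distribution | p | Kept | Lost |
|---|---|---|---|
| Normal, median 65 | 0.50 | 0.3989² / 0.25 = 0.637 | 36.3% |
| Normal, mean 60, SD 12 | 0.662 | 0.3658² / 0.224 = 0.598 | 40.2% |
| Normal, mean 70, SD 10 | 0.309 | 0.3521² / 0.213 = 0.581 | 41.9% |
| Normal, 30% or 70% under 65 | 0.30 or 0.70 | 0.3477² / 0.21 = 0.576 | 42.4% |
| Flat, 40–90 | 0.50 | 3 × 0.25 = 0.750 | 25.0% |
| Flat, 30–90 | 0.583 | 3 × 0.243 = 0.729 | 27.1% |

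For normal age the smallest possible loss is 1 − 2/π = 36.3%, reached when 65 is the median.

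**Step 3: power of the interaction test.** Take an interaction that continuous age would detect with 80% power. Its standardized effect is 1.96 + 0.842 = 2.802. After the split, power is Φ(2.802 × √kept − 1.96).

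- Normal, median 65: Φ(2.236 − 1.96) = 61%.
- Flat, 40–90: Φ(2.426 − 1.96) = 68%.
- Normal, 30% or 70% under 65: Φ(2.126 − 1.96) = 57%.

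Starting from 90% power, the first two become 73% and 80%.

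**Step 4: the opposite case.** The squared correlation is symmetric. If the true effect were a step exactly at 65, the split would lose nothing, and the linear term would be the one to lose 36% (normal, median 65) or 25% (flat, 40–90).

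**The case against.** The strongest reply is that the planned split is defensible. A cut fixed in advance prevents a search for cut-points, and testing the interaction on the same two groups makes the p-value match the two hazard ratios shown beside it. A continuous test examines a different contrast, so the remedy has a small cost. That stands, and labelling the p-value deals with it. If the effect does change near 65, the split is the better test (Step 4). That also stands, but the plan gives no reason to expect a step at that age, and the spline check and the retained subgroup estimates would help to show one.

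The list in Section 12.3.2 is open, so a continuous analysis is already allowed, and Section 12.3.4 provides for an amended SAP before the blind is broken. Allowing an analysis is not the same as pre-specifying it, however: a coding chosen after the data are seen carries less weight.

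A reader might infer two stronger points that the documents do not support. The first is that the split also enters the three predictor models for ATP use, bradycardia pacing and CRT-D need. Section 12.1.6.1 says only: "Covariates considered for inclusion in the final multivariate models include, but are not limited to, the characteristics listed in Section 12.3.2". Section 12.3.2 distinguishes characteristics from their subgroups, and this cross-reference takes the characteristics. The coding of age in those models is therefore unspecified, and a claim of residual confounding there has no basis. The second is that more than a third of the information is lost whatever the ages turn out to be. That needs roughly normal age and a linear effect, and the documents establish neither.

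**Conclusion.** The point holds as a minor improvement to the subgroup analyses. The only age coding named for the interaction test is a split at 65, with no stated reason and no design constraint behind it. Given an effect roughly linear in age, the split loses about 36–42% of the information for normal age and about 25–27% for flat age. With the cut at the median, 80% power on continuous age falls to about 61% (normal) or 68% (flat); at the unfavourable end of the normal cases it falls to about 57%. Given a threshold near 65, little is lost.

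No endpoint conclusion, stopping rule or alpha allocation uses the age split, so the primary endpoint's sample size, power and type I error are unaffected.

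**What to change.** State in Section 12.3.2 that the arm-by-age interaction will be tested with age as a continuous linear term for the primary and secondary endpoints, with a spline model as a sensitivity check for curvature. Keep the hazard ratios for 65 and over and under 65 in the subgroup table, and label the interaction p-value as coming from the continuous-age model, since it does not test the difference between the two displayed estimates.

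The cost is a sentence or two in the SAP before the blind is broken, plus the table label and one extra sensitivity model. No new data are needed.

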12.3.3. Justification of Pooling

The study will be conducted globally. A Cox proportional hazards model for the Primary Endpoint will be performed, evaluating geography (e.g., continent) as a covariate in the model, to assess the poolability of the patients from different geographies.

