12.1.1.1. Hypotheses

The hazard ratio of all-cause shocks will be used to evaluate the equivalence of shocks only programming and standard therapy. A relative equivalence margin of 35% in each direction will be employed. The following hypotheses will be used.

H₀: Hazard Ratio ≤ 0.65 or Hazard Ratio $\geq (1/0.65)$

 H_A : 0.65 < Hazard Ratio < (1/0.65)

12.1.1.2. Sample Size

A total of 2600 subjects – 1300 per group – will be required to sufficiently power the primary endpoint. The sample size of 2600 subjects will provide the number of primary endpoint events necessary to power the Primary Endpoint. Two assumption scenarios were considered to determine the required sample size.

	Scenario 1	Scenario 2
Expected all-cause shock rate in each group	6%	7%
Alpha	5%	5%
Power	90%	90%
Equivalence Margin	(0.65 - [1/0.65]) = (0.65 - 1.54)	(0.65 - [1/0.65]) = (0.65 - 1.54)
Attrition at 18 months	10%	10%
Enrollment Period	42 months	42 months
Follow-up Period	First Patient: 60 months	First Patient: 54 months
Tonow-up Terrou	Final Patient: 18 months	Final Patient: 12 months
Maximum Trial Duration	60 months	54 months

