12.1.1.3. Statistical Methods

All implanted and randomized subjects will contribute to the analysis of the Primary Endpoint. Cox proportional hazards modeling will be performed, with time-to-first shock therapy episode used as the outcome and programming scheme used as the covariate in the model. Traditional therapy will be considered the reference group in the analysis. Each subject's first shock therapy episode will contribute to the analysis. Subjects without a shock therapy episode will be censored at their date of death, withdrawal, study exit or on the date of the data snapshot, whichever occurs first. From the Cox model, the hazard ratio and corresponding confidence interval for programming scheme will be calculated. If the confidence interval for the hazard ratio is fully contained within the equivalence region – between 0.65 and 1.54 – equivalence of shocks only and standard programming will be concluded.

If equivalency cannot be established, further testing for superiority will be performed without need for a multiplicity adjustment to the significance level of the test beyond the adjustment necessary to accommodate the interim superiority tests. This additional testing is possible because the equivalence test is comprised of two separate one-sided non-inferiority tests. If non-inferiority is established for only one of the two one-sided non-inferiority tests, superiority can further be tested, per gating methodology.

The following table outlines the possible results and conclusions that can be drawn from the Primary Endpoint analysis.

Result of Lower Confidence Limit of Confidence Interval	Result of Upper Confidence Limit of Confidence Interval	Conclusion
>0.65	<1.54	Equivalence of shocks only to standard therapy
≤0.65	≥1 and <1.54	Non-inferiority of shocks only to standard therapy
<0.65	<1	Superiority of shocks only to standard therapy
≤1 and >0.65	>1.54	Non-inferiority of standard therapy to shocks only
>1	>1.54	Superiority of standard therapy to shocks only

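### The pooling check in section 12.3.3 tests whether shock rates differ by region, not whether the treatment hazard ratio does

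*Combined protocol and SAP*

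**What the plan says.** Section 12.3.3 notes that "The study will be conducted globally" and gives one method for justifying pooling: a Cox model for the primary endpoint, "evaluating geography (e.g., continent) as a covariate in the model, to assess the poolability of the patients from different geographies". It does not list the other model terms, fix the regions, or give a test level or a consequence if regions differ.

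Three other sections help to read that sentence:

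- Section 12.1.1.3 has "programming scheme used as the covariate in the model". There the word denotes a single model term.
- Section 12.3.2 deals with treatment-effect heterogeneity in different words: "Analyses will be performed to assess whether significant interactions exist between randomization group and various baseline characteristics". Its table covers age, gender, atrial fibrillation, ischemic status and diabetes, but not geography. The list is open: "Analyses will evaluate, but are not limited to, the following baseline characteristics and their corresponding subgroups".
- Section 8.2 states that randomization "will be stratified by ischemic etiology, history of atrial fibrillation, and diabetes". Region is not a stratification factor.

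The primary conclusion rests on the overall interval alone: "If the confidence interval for the hazard ratio is fully contained within the equivalence region", equivalence is concluded (section 12.1.1.3).

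**The concern.** The trial pools a treatment contrast, the hazard ratio of shock only against ATP and shock. Pooling is reasonable if that contrast is similar across regions. A geography coefficient says something else: whether patients in one region are shocked more often than patients in another, averaged over arms.

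The check can therefore mislead in both directions. It can look reassuring when the arms have opposite effects in different regions, and worrying when regions differ only in background shock rate. The first direction matters more in an equivalence trial, because opposite regional effects average towards a hazard ratio of 1, which is the result that leads to a claim of equivalence.

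**Working it through.** **Model.** For two regions, write the hazard as λ₀(t)·exp(β·arm + γ·geography + δ·arm×geography). The regional hazard ratios are exp(β) and exp(β+δ). Entering geography as a covariate tests γ in the model without δ. Whether one hazard ratio fits both regions is the question δ = 0.

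**Event count.** Section 12.3.3 gives no figure, so the sample size in section 12.1.1.2 was reproduced first to set a realistic number of events. Inputs from that table (scenario 1): 2600 subjects, margin 0.65 to 1/0.65, power 90%, "Expected all-cause shock rate in each group" 6%, attrition 10% at 18 months, 42-month enrollment, follow-up 18 to 60 months. The final significance level of 0.022 is from section 12.3.1. The table gives no time unit for the 6%.

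- Events needed for two one-sided tests at a true hazard ratio of 1: 4(2.014 + 1.645)²/(ln 0.65)² = 288.6.
- Expected events with 6% read as an 18-month risk: shock hazard −ln(0.94)/1.5 = 0.0413 per year and attrition hazard −ln(0.90)/1.5 = 0.0702 per year. With follow-up uniform over 1.5 to 5 years, 2600 subjects give 288.1 events.
- N for 90% power is then 2604 (2590 under scenario 2), against the stated 2600. With 6% read as annual, 2600 subjects give 418 events and about 98% power, which does not reproduce the plan.

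The 18-month reading is therefore the main case; annual-rate results are in brackets below.

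**Simulation.** 1500 trials per setting (Monte Carlo standard error at most 1.3 points), 2600 subjects, 1:1 arms in each region, exponential shock and attrition times, follow-up uniform over 18 to 60 months, no interim stopping. The overall mean hazard was held fixed, giving about 287 [417] events. Tests are 5% Wald tests. The geography term comes from the model with arm and geography; the interaction comes from the model that adds arm×geography. A dash means not reported.

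| Setting | Geography term significant | Interaction significant |
|---|---|---|
| Equal regions, equal average hazards, HR 0.65 vs 1.54 | 5% [5%] | 96% [99%] |
| Equal regions, equal average hazards, HR 0.60 vs 1.67 | 5% [4%] | 99% [>99%] |
| Equal regions, no arm effect, hazards differ 1.5-fold | 93% [98%] | 5% [6%] |
| Equal regions, no arm effect, hazards differ 1.25-fold | 45% [63%] | 5% [5%] |
| Equal regions, HR 0.80 vs 1.25 | – | 47% [65%] |
| HR 0.90 in 80% of subjects, 1.67 in 20% | – | 55% [70%] |

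In the 0.60 versus 1.67 setting both regions lie outside the margin. Overall equivalence (95% interval from the arm-only model inside 0.65 to 1/0.65) is still concluded in 91% [98%] of trials, and in 86% [94%] it is concluded together with a non-significant geography term.

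**Cross-checks (18-month reading).**

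- With equal regions the standard error of the log ratio of hazard ratios is about 4/√288 = 0.236. For 0.80 versus 1.25 the log ratio is 2 × 0.223 = 0.446, so z = 1.89 and power is Φ(1.89 − 1.96) = 47%.
- For 0.65 versus 1.54, summing reciprocal events over the four cells gives 94–95% power. With a 70:30 regional split the two powers fall to 40–42% and 90–92%.
- A separate 600-run simulation gave 4.0% and 96.3% for the first row of the table. For the 1.5-fold setting it gave 97.2% and 5.2%. It raised one region above a fixed baseline (354 events) instead of holding the mean hazard fixed, which would account for 97% rather than 93%.

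**The case against.** The strongest objection is textual. Section 12.3.3 does not say main effect and does not exclude an arm-by-geography term. The model in section 12.1.1.3 has only one covariate, so its use of the word proves little about a larger model. The stated aim is whether patients can be pooled, and regional shock rates do bear on that. The list in section 12.3.2 is open and section 12.3.4 allows the analysis plan to be amended before unblinding, so a geography interaction could still be added. No trial decision depends on the check.

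The settings are also extreme. Opposite effects on or beyond both margins that cancel almost exactly are not suggested anywhere in the plan, and the required tachycardia programming is the same at all sites apart from the discretionary type of detection enhancement.

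Much of this stands. The wording permits an interaction, the primary decision is unaffected, and the large contrasts show what the check cannot see, not what is expected. What remains is that a geography main effect does not measure heterogeneity of the arm effect, that the plan uses separate words when it means interaction, and that it nowhere commits to an arm-by-geography analysis or ties one to pooling.

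**Conclusion.** The concern holds. On its plain reading, the only analysis offered to justify pooling has about a 5% chance of flagging regional hazard ratios at opposite ends of the equivalence margin when average hazards are equal, and a 93% chance of flagging a 1.5-fold difference in shock rate that has no bearing on the arm effect.

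These percentages assume two equal regions, a 5% test level and an 18-month shock rate, none of which the plan states. The defect is one of method and depends on none of them. It affects how the pooled result is supported and interpreted, not the validity of the primary decision. It is a worthwhile correction, and confidence is moderate because section 12.3.3 is brief enough to allow another reading.

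**What to change.** In section 12.3.3:

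- Fit arm, geography and arm-by-geography for the primary endpoint. Define the regions, and a rule for merging small ones, before unblinding.
- Base the poolability assessment on the interaction together with region-specific hazard ratios and 95% confidence intervals, displayed against 0.65 to 1.54. Keep the geography coefficient as a description of regional shock rates.
- State the interaction test level and the consequence in advance: regional results are reported beside the overall hazard ratio, and the primary decision rule does not change.
- Leave the primary Cox model in section 12.1.1.3 as it is. A region-stratified Cox model can be a pre-specified sensitivity analysis, but not a change triggered by the data.

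The cost is a short paragraph in the statistical analysis plan and no new data. The limitation should be stated there. With about 288 events and two equal regions, 80% power needs a ratio of regional hazard ratios of about exp(2.80 × 0.236) = 1.9, and small regions lower power further. A non-significant interaction therefore does not show homogeneity, which is why the regional estimates and intervals must accompany the test.
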